#### **5.6.2.14. Recording of AEs and SAEs**

- Refer to Section 8.2 for procedures for the investigator to record AEs and SAEs. Refer to Section 8.3 for guidelines and how to report SAE reports to GSK Biologicals.
- The subjects' parent(s)/LAR(s) will be instructed to contact the investigator immediately should the subjects manifest any signs or symptoms they perceive as serious.
- Record large injection site reactions as described in 8.1.3.1.
- At the vaccination visit (Visit 2), diary cards will be provided to the subject's parent(s)/LAR(s). The subject's parent(s)/LAR(s) will record body (axillary/rectal) temperature and any solicited local/general AEs (i.e., on the day of vaccination and during the next three days) or any unsolicited AEs (i.e., on the day of vaccination and during the next 30 days) occurring after vaccination. The subject's parent(s)/LAR(s) will be instructed to return the completed diary card to the investigator at the next study visit.
- Collect and verify completed diary cards during discussion with the subject's parent(s)/LAR(s) at Visit 3.
- Any unreturned diary cards will be sought from the subject's parent(s)/LAR(s) through telephone call(s) or any other convenient procedure. The investigator/*designee* will transcribe the collected information into the eCRF in English. **(Amended 12 December 2016)**

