**Table 14 Intensity scales for solicited symptoms**

Adverse Event	Intensity grade	Parameter
Pain at injection site	0	None
	1	Mild: Minor reaction to touch
	2	Moderate: Cries/protests on touch
	3	Severe: Cries when limb is moved/spontaneously painful
Redness at injection site		Record greatest surface diameter in mm
Swelling at injection site		Record greatest surface diameter in mm
Fever*		Record temperature in °C/°F
Irritability/Fussiness	0	Behaviour as usual
	1	Mild: Crying more than usual/no effect on normal activity
	2	Moderate: Crying more than usual/interferes with normal activity
	3	Severe: Crying that cannot be comforted/prevents normal activity
Drowsiness	0	Behaviour as usual
	1	Mild: Drowsiness easily tolerated
	2	Moderate: Drowsiness that interferes with normal activity
	3	Severe: Drowsiness that prevents normal activity
Loss of appetite	0	Appetite as usual
	1	Mild: Eating less than usual/no effect on normal activity
	2	Moderate: Eating less than usual/interferes with normal activity
	3	Severe: Not eating at all

\*Fever is defined as temperature  $\geq 37.5^{\circ}\text{C}/99.5^{\circ}\text{F}$  for oral, axillary or tympanic route, or  $\geq 38.0^{\circ}\text{C}/100.4^{\circ}\text{F}$  for rectal route. The preferred route for recording temperature in this study will be axillary/rectal.

The maximum intensity of local injection site redness/swelling will be scored at GSK Biologicals as follows:

- 0 : Absent
- 1 :  $\leq 5$  mm
- 2 :  $> 5$  mm and  $\leq 20$  mm
- 3 :  $> 20$  mm

The maximum intensity of fever (*oral, axillary or tympanic route*) will be scored at GSK Biologicals as follows: (Amended 12 December 2016)

- 0 =  $< 37.5^{\circ}\text{C}$
- 1 =  $\geq 37.5^{\circ}\text{C}$  to  $\leq 38.0^{\circ}\text{C}$
- 2 =  $> 38.0^{\circ}\text{C}$  to  $\leq 39.0^{\circ}\text{C}$
- 3 =  $> 39.0^{\circ}\text{C}$

The investigator will assess the maximum intensity that occurred over the duration of the event for all unsolicited AEs (including SAEs) recorded during the study. The assessment will be based on the investigator's clinical judgement.

The intensity should be assigned to one of the following categories:

- 1 (mild) = An AE which is easily tolerated by the subject, causing minimal discomfort and not interfering with everyday activities.
- 2 (moderate) = An AE which is sufficiently discomforting to interfere with normal everyday activities.

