5.4. Analysis of safety and reactogenicity

5.4.1. Analysis of safety and reactogenicity planned in the protocol

The primary analysis will be based on the TVC. If more than 5% of enrolled subjects are excluded from the ATP cohort for analysis of safety, then a second analysis based on this ATP cohort will be performed to complement the TVC analysis. All analyses will be descriptive.

- The percentage of subjects with at least one local symptom (solicited or unsolicited), with at least one general symptom (solicited or unsolicited) and with any symptom (solicited or unsolicited) during the 4-day (Day 0-Day 3) solicited follow-up period will be tabulated with exact 95% CI [Clopper, 1934]. The same calculations will be done for symptoms (solicited or unsolicited) rated as grade 3 in intensity, for symptoms (solicited or unsolicited) leading to medical advice and for symptoms (solicited or unsolicited) assessed as causally related to vaccination.
- The incidence of local AEs (solicited and unsolicited) will be calculated at each injection site as well as overall (all sites considered) for each group.
- The percentage of subjects reporting each individual solicited local and general symptom during the 4-day (Day 0-Day 3) solicited follow-up period will be tabulated after the vaccine dose, with exact 95% CI [Clopper, 1934]. The same calculations will be done for each individual solicited symptom rated as grade 3 in intensity and for each individual solicited symptom assessed as causally related to vaccination.
- All computations mentioned above will be done for Grade ≥ 2 (solicited symptoms only) and grade 3 symptoms, for symptoms considered related to vaccination (general symptoms only), for grade 3 symptoms considered related to vaccination (general symptoms only) and for symptoms that resulted in a medically-attended visit.
- Occurrence of fever and related fever will be reported per 0.5°C cumulative temperature increments as well as the occurrence of grade 3 fever ($> 39.0^{\circ}\text{C}$ axillary temperature) with causal relationship to vaccination.

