10. ANNEXES

10.1. Business rules for standard data derivations and statistical methods

This section contains GSK Vaccines' standard rules for data display and derivation for clinical and epidemiological studies. These rules will be applied along with those detailed in section 9 (additional study-specific rules).

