10.1.3.5. Temperature

- Temperatures will be presented in degrees Celsius (°C). Temperatures reported in degrees Fahrenheit (°F) will be converted as follows:

$$\text{Temperature (Celsius)} = ((\text{Temperature (Fahrenheit)} - 32) \times 5) / 9$$

The result is rounded to 1 decimal.

- The intensity of fever measured by oral, axillary or tympanic route will be scored as defined in the protocol. If in case, measured by rectal route, then the scoring will be performed as below to integrate the results with the other routes.

0	<38°C
1	≥38.0°C to ≤39.0°C
2	>39.0°C to ≤40.0°C
3	>40.0°C

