Compliance % = (number of doses with symptom sheet return / number of administered doses) X 100

Template 17 Percentage and nature of <grade 3>symptoms (solicited and unsolicited) reported during the 4-day (Days 0-3) post-vaccination period following each dose and overall (Total vaccinated cohort)

Group	Any symptom					General symptoms					Local symptoms				
	N	n	%	95% CI		N	n	%	95% CI		N	n	%	95% CI	
				LL	UL				LL	UL				LL	UL
dTpa group	335	264	78.8	74.0	83.1	335	134	40.0	34.7	45.5	335	250	74.6	69.6	79.2
Control group	336	279	83.0	78.6	86.9	336	151	44.9	39.5	50.4	336	264	78.6	73.8	82.8

dTpa Group = This group will consist of infants born to mothers belonging to the dTpa Group in study 116945 [DTPA (BOOSTRIX)-047]. All subjects in this group will receive *Infanrix hexa* co-administered with *Prevenar 13* according to the routine national immunisation schedule.

Control Group: This group will consist of infants born to mothers belonging to the Control group in study 116945 [DTPA (BOOSTRIX)-047]. All subjects in this group will receive *Infanrix hexa* co-administered with *Prevenar 13* according to the routine national immunisation schedule.

For each dose and overall/subject:

N= number of subjects with at least 1 administered dose

n(%) = number(percentage) of subjects presenting at least 1 type of symptom whatever the study vaccine administered

For overall/dose:

N= number of administered doses

n(%) = number(percentage) of doses followed by at least 1 type of symptom whatever the study vaccine administered

95% CI = exact 95% confidence interval, LL = Lower Limit, UL = Upper Limit

Template 18 Percentage of solicited local symptoms reported during the 4-day (Day 0-3) post-vaccination period following each dose and overall (Total vaccinated cohort)

Symptom	Type	dTpa group					Control group				
		N	n	%	LL	UL	N	n	%	LL	UL
Pain	All	330	237	71.8	66.6	76.6	329	248	75.4	70.4	79.9
	Grade 3	330	24	7.3	4.7	10.6	329	20	6.1	3.8	9.2
	Medical advice	330	0	0.0	0.0	1.1	329	0	0.0	0.0	1.1
Redness (mm)	All	330	113	34.2	29.1	39.6	329	94	28.6	23.8	33.8
	Grade 3	330	4	1.2	0.3	3.1	329	1	0.3	0.0	1.7
	Medical advice	330	0	0.0	0.0	1.1	329	0	0.0	0.0	1.1
Swelling (mm)	All	330	98	29.7	24.8	34.9	329	90	27.4	22.6	32.5
	Grade 3	330	6	1.8	0.7	3.9	329	5	1.5	0.5	3.5
	Medical advice	330	0	0.0	0.0	1.1	329	0	0.0	0.0	1.1

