dTpa Group = This group will consist of infants born to mothers belonging to the dTpa Group in study 116945 [DTPA (BOOSTRIX)-047]. All subjects in this group will receive *Infanrix hexa* co-administered with *Prevenar 13* according to the routine national immunisation schedule.

Control Group: This group will consist of infants born to mothers belonging to the Control group in study 116945 [DTPA (BOOSTRIX)-047]. All subjects in this group will receive *Infanrix hexa* co-administered with *Prevenar 13* according to the routine national immunisation schedule.

For overall/subject:

N= number of subjects with at least 1 documented dose

n(%) = number(percentage) of subjects reporting the symptom at least once

95%CI= Exact 95% confidence interval; LL = lower limit, UL = upper limit

Template 19 Percentage of solicited general symptoms reported during the 4-day (Days 0-3) post-vaccination period following each dose and overall (Total vaccinated cohort)

		dTpa group					Control group				
Symptom	Type	N	n	%	95 % CI		N	n	%	95 % CI	
					LL	UL				LL	UL
Overall/subject											
Drowsiness	All										
	Grade 2 or 3										
	Grade 3										
	Related										
	Grade 3*Related										
	Medical advice										
Irritability	All										
	Grade 2 or 3										
	Grade 3										
	Related										
	Grade 3*Related										
	Medical advice										
Loss of appetite	All										
	Grade 2 or 3										
	Grade 3										
	Related										
	Grade 3*Related										
	Medical advice										
Temperature/(Axillary) (°C)	All										
	>37.5										
	>38.0										
	>38.5										
	>39.0										
	>39.5										
	Related										
	>39*Related										
	Medical advice										

dTpa Group = This group will consist of infants born to mothers belonging to the dTpa Group in study 116945 [DTPA (BOOSTRIX)-047]. All subjects in this group will receive *Infanrix hexa* co-administered with *Prevenar 13* according to the routine national immunisation schedule.

Control Group: This group will consist of infants born to mothers belonging to the Control group in study 116945 [DTPA (BOOSTRIX)-047]. All subjects in this group will receive *Infanrix hexa* co-administered with *Prevenar 13* according to the routine national immunisation schedule. For each dose and overall/subject:

N= number of subjects with at least 1 documented dose

n(%) = number(percentage) of subjects reporting the symptom at least once

For overall/subject:

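### The SAP's rectal fever scale implies a 0.5 °C route difference at fever onset but 1.0 °C at grades 2 and 3, so no constant offset makes pooled fever grades comparable across routes

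*SAP*

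**What the plan says.** Protocol Table 14 defines fever as 37.5 °C or more by oral, axillary or tympanic route, and 38.0 °C or more rectally. It then grades intensity for the three non-rectal routes only: grade 1 from 37.5 to 38.0, grade 2 above 38.0 to 39.0, grade 3 above 39.0 °C. It gives no rectal grades and no conversion between routes.

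SAP 10.1.3.5 fills the gap: "If in case, measured by rectal route, then the scoring will be performed as below to integrate the results with the other routes". Rectal grade 1 is "≥38.0°C to ≤39.0°C", grade 2 is above 39.0 to 40.0, and grade 3 is above 40.0 °C. No reason is given for these limits. The scale sits under SAP 10.1, which holds the sponsor's "standard rules for data display and derivation for clinical and epidemiological studies".

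Rectal measurement is an expected route. Protocol Table 14 states: "The preferred route for recording temperature in this study will be axillary/rectal". Under Protocol 5.6.2.14 parents "will record body (axillary/rectal) temperature" in the diary.

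For reporting, SAP 5.4.1 says: "Occurrence of fever and related fever will be reported per 0.5°C cumulative temperature increments as well as the occurrence of grade 3 fever", with grade 3 given as above 39.0 °C axillary. It also asks for grade ≥2 and grade 3 computations for solicited symptoms. Template 17 is a composite of grade 3 "symptoms (solicited and unsolicited) reported during the 4-day (Days 0-3) post-vaccination period following each dose and overall". Template 19 has a single temperature block, labelled axillary.

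**The concern.** Pooling grades across routes makes sense only if a grade stands for about the same severity whichever route was used. Here the rectal grade 1 band is 1.0 °C wide and the other-route band is 0.5 °C wide, so one scale is not a shifted copy of the other. If the true route difference is close to the 0.5 °C in the protocol's fever definition, an infant measured rectally needs a higher equivalent temperature to reach grade 2 or 3 than an infant measured in the axilla. Pooled grade ≥2 and grade 3 fever would then be too low by an amount that depends on how many families use the rectal route.

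Fever is a named safety interest. Protocol 1.3.1 lists temperature of 40.0 °C or more as an identified risk of Infanrix hexa, and Protocol 6.6 notes higher febrile rates when it is given with a pneumococcal conjugate vaccine.

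**Working it through.** **Inputs.** Other-route lower limits, Protocol Table 14: 37.5, 38.0, 39.0 °C. Rectal lower limits, SAP 10.1.3.5: 38.0, 39.0, 40.0 °C. The plan states no offset to reproduce, so offsets d are taken as assumptions over the range 0.0–1.5 °C.

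**Implied offset at each limit (rectal minus other route).**
- Fever onset: 38.0 − 37.5 = 0.5 °C
- Grade 2: 39.0 − 38.0 = 1.0 °C
- Grade 3: 40.0 − 39.0 = 1.0 °C

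**Which constant offset fits the protocol's fever definition?** Rectal 38.0 must match 37.5 by another route: 38.0 − d = 37.5, so d = 0.5 °C. With d = 1.0 °C, rectal 38.0 matches 37.0 °C, which is not fever.

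**Grade comparison.** Each rectal reading t from 36.5 to 41.9 °C, in 0.1 °C steps, was graded by the SAP scale. The value t − d was graded by Table 14. The count is the number of readings on which the two grades differ. The last column repeats this for a single-offset rectal scale with limits ≥38.0, >38.5 and >39.5 °C.

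| Offset d (°C) | SAP scale: graded lower | SAP scale: graded higher | SAP scale: total | Single-offset scale: total |
|---|---|---|---|---|
| 0.0 | 25 | 0 | 25 | 15 |
| 0.3 | 16 | 0 | 16 | 6 |
| 0.5 | 10 | 0 | 10 | 0 |
| 0.7 | 6 | 2 | 8 | 6 |
| 0.8 | 4 | 3 | 7 | 9 |
| 0.9 | 2 | 4 | 6 | 12 |
| 1.0 | 0 | 5 | 5 | 15 |
| 1.1 | 0 | 8 | 8 | 18 |
| 1.5 | 0 | 20 | 20 | 26 |

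The SAP scale never reaches zero; its minimum is 5, at d = 1.0 °C.
- At d = 0.5 °C, rectal 38.6–39.0 is scored grade 1 but matches 38.1–38.5 (grade 2), and rectal 39.6–40.0 is scored grade 2 but matches 39.1–39.5 (grade 3).
- At d = 1.0 °C, grades 2 and 3 agree, but rectal 38.0–38.4 is scored grade 1 although it matches 37.0–37.4 (no fever).

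**Bound on the pooled grade 3 rate.** Let r be the share of infants measured rectally. Assume the same fever distribution in both route groups after a 0.5 °C shift. Let k (0 ≤ k ≤ 1) be the fraction of rectal readings above 39.5 °C that also exceed 40.0 °C. The ratio of the SAP-graded rate to the consistently graded rate is (1 − r) + r·k, which is at least 1 − r. The relative under-count is therefore at most 1% at r = 1%, 5% at r = 5%, 25% at r = 25% and 50% at r = 50%. The same bound holds for grade ≥2, with k defined at 38.5 and 39.0 °C. These are worst cases at k = 0, not estimates.

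**The case against.** The strongest reply is that nothing in the documents requires a constant offset. Fever grade is an ordinal convention: Table 14 already puts oral, axillary and tympanic readings on one scale without conversion. The 0.5 °C appears only as a difference between two onset definitions. The single-offset scale's zero mismatches at 0.5 °C are true by construction, and from 0.8 °C upwards the SAP scale agrees better (7 against 9 at 0.8 °C, 5 against 15 at 1.0 °C). The documents do not give the true offset.

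Much of this stands. No stated limit is breached, and the single-offset scale cannot be shown to be closer to physiology. What does not follow is that the rule is coherent. A 1.0 °C offset rescues grades 2 and 3 only by counting as fever rectal readings whose other-route match is not fever. The 0.5 °C offset is the only constant one compatible with the protocol's fever definition.

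Two further replies narrow the reach. In the Template 19 shell, temperature has increment rows and no grade 2 or grade 3 rows, so in the shells the rectal grade enters mainly through the Template 17 composite. An infant is lost there only if no other grade 3 symptom was reported. The text of SAP 5.4.1 does, however, ask for individual grade ≥2 and grade 3 symptoms.

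A reader might also infer from the label "Temperature/(Axillary) (°C" in Template 19 that rectal 39.1–40.0 °C will be counted above 39.0 °C while scored grade 2. That would follow only if rectal readings enter unadjusted. The plan does not say so, and SAP section 12 describes the shells as illustrative and to be adapted.

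**Conclusion.** The pooling rule is internally inconsistent, and this is a minor defect. The implied offsets of 0.5, 1.0 and 1.0 °C are exact, and nothing elsewhere in the documents resolves them. Against the protocol's 0.5 °C onset difference, ten rectal readings at 0.1 °C resolution are graded one level low, and pooled grade ≥2 and grade 3 fever can be under-counted.

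The size in practice is unknown, because neither the true offset nor the rectal share is given. The output affected is a descriptive secondary one and concerns absolute rates.

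Two stronger readings are tempting. One is that severe fever will be materially under-reported: with r unknown this cannot be shown, and the effect is negligible if r is small. The other is that the comparison of maternal groups is biased: that would need different rectal use by group, which nothing in the documents suggests.

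**What to change.** In SAP 10.1.3.5 and 5.4.2:
- Report graded fever and the 0.5 °C increments by route as well as pooled.
- Grade pooled fever with one offset consistent with the protocol's fever definition: rectal grade 1 ≥38.0 to ≤38.5, grade 2 >38.5 to ≤39.5, grade 3 >39.5 °C. If the sponsor keeps its standard scale as the main one, give the reason and run this grading as a stated sensitivity analysis.
- Subtract the same 0.5 °C from rectal readings in any pooled increment rows, including the row for related fever above 39 °C.

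The cost is SAP wording and a re-derivation from temperatures and routes that scoring already needs. The downside is slightly less comparability with other studies graded on the sponsor's standard scale, which the by-route table largely covers. The SAP should also say that 0.5 °C is the protocol's onset difference and not a validated conversion at higher temperatures.

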## 10.8. Analysis of safety

The primary analysis will be based on the TVC. If more than 5% of enrolled subjects are excluded from the ATP cohort for analysis of safety, then a second analysis based on this ATP cohort will be performed to complement the TVC analysis. All analyses will be descriptive.

- The percentage of subjects with at least one local symptom (solicited or unsolicited), with at least one general symptom (solicited or unsolicited) and with any symptom (solicited or unsolicited) during the 4-day (Day 0-Day 3) solicited follow-up period will be tabulated with exact 95% CI [Clopper, 1934]. The same calculations will be done for symptoms (solicited or unsolicited) rated as grade 3 in intensity, for symptoms (solicited or unsolicited) leading to medical advice and for symptoms (solicited or unsolicited) assessed as causally related to vaccination.
- The incidence of local AEs (solicited and unsolicited) will be calculated at each injection site as well as overall (all sites considered) for each group.
- The percentage of subjects reporting each individual solicited local and general symptom during the 4-day (Day 0-Day 3) solicited follow-up period will be tabulated after the vaccine dose, with exact 95% CI [Clopper, 1934]. The same calculations will be done for each individual solicited symptom rated as grade 3 in intensity and for each individual solicited symptom assessed as causally related to vaccination. **(Amended 12 December 2016)**
- All computations mentioned above will be done for Grade  $\geq 2$  (solicited symptoms only) and grade 3 symptoms, for symptoms considered related to vaccination (general symptoms only), for grade 3 symptoms considered related to vaccination (general symptoms only) and for symptoms that resulted in a medically-attended visit.
- Occurrence of fever and related fever will be reported per 0.5°C cumulative temperature increments as well as the occurrence of grade 3 fever ( $> 39.0^{\circ}\text{C}$  axillary temperature) with causal relationship to vaccination.

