10.1.2.3.2. Studies with paper diaries

For studies using paper diaries which have questions in the CRF indicating the presence or absence of solicited symptoms, the following rules are applicable.

Denominators for the summary of local (or general) solicited symptoms will be calculated using the number of subjects who respond "Yes" or "No" to the question concerning the occurrence of local (or general) symptoms.

When a specific symptom is marked as having not occurred following a specific vaccination for the specified post-vaccination period for the symptom in question, all daily measurements will be imputed as Grade 0.

When a specific symptom is marked as having occurred following a specific vaccination for the specified post-vaccination period for the symptom in question, any missing daily recordings will be given imputed values to allow them to contribute to the ‘Any’ rows but not to specific grade rows of the symptom summary tables.

When the occurrence of a specific symptom is not present (for the specified post-vaccination period for the symptom in question) but the group of symptoms (local or general) is marked as having occurred, all missing daily recordings will be given imputed values to allow them to contribute to the ‘Any’ rows but not to specific grade rows of the symptom summary tables.

The following table shows how subjects contribute to each category for a specific solicited symptom over the Day 0 to Day 3 post-vaccination period:

Solicited symptom category	Subjects included in the calculation of the numerator
Any	All subjects with at least one occurrence of the symptom at grade 1, grade 2, or grade 3 between Day 0 and Day 3 or with the symptom marked as present and at least one missing daily recording between Day 0 and Day 3
At least grade 1	All subjects with at least one occurrence of the symptom at grade 1, grade 2, or grade 3 between Day 0 and Day 3
At least grade 2	All subjects with at least one occurrence of the symptom at grade 2 or grade 3 between Day 0 and Day 3
At least grade 3	All subjects with at least one occurrence of the symptom at grade 3 between Day 0 and Day 3

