For a given subject and the analysis of solicited adverse events within 4 days post-vaccination, missing or non-evaluable measurements will not be replaced. Therefore, the analysis of the solicited adverse events based on the Total Vaccinated Cohort will include only vaccinated subjects for doses with documented safety data (i.e., symptom screen completed). More specifically the following rules will be used:

- Subjects who documented the absence of a solicited adverse events after one dose will be considered not having that adverse events after that dose.
- Subjects who documented the presence of a solicited symptom and fully or partially recorded daily measurement over the solicited period will be included in the summaries at that dose and classified according to their maximum observed daily recording over the solicited period.
- Subjects who documented the presence of a solicited symptom after one dose without having recorded any daily measurement will be assigned to the lowest intensity category at that dose (i.e., 37.5°C for fever or grade 1 for other symptoms).
- Doses without symptom sheets documented will be excluded.

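### Does the SAP's separate rectal fever scale leave the pooled grade 2-or-higher and grade 3 fever rates undefined?

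*SAP*

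**What the plan says.** Protocol section 8.2.3.2.1 (Table 14 and the lists below it) counts a temperature as fever from 37.5 °C by the oral, axillary or tympanic route and from 38.0 °C by the rectal route. The intensity scale that follows covers the first three routes only: grade 1 from 37.5 to 38.0 °C, grade 2 above 38.0 and up to 39.0 °C, grade 3 above 39.0 °C. Rectal readings are nevertheless expected. The Table 14 footnote says "The preferred route for recording temperature in this study will be axillary/rectal", and under protocol section 5.6.2.14 the parents "will record body (axillary/rectal) temperature and any solicited local/general AEs" after vaccination.

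SAP section 10.1.3.5 fills the gap. It keeps the protocol scale for the other routes ("The intensity of fever measured by oral, axillary or tympanic route will be scored as defined in the protocol"). For temperature "measured by rectal route, then the scoring will be performed as below to integrate the results with the other routes" it sets grade 1 from 38.0 to 39.0 °C, grade 2 above 39.0 and up to 40.0 °C, and grade 3 above 40.0 °C.

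On reporting, SAP section 5.4.1 states: "Occurrence of fever and related fever will be reported per 0.5°C cumulative temperature increments as well as the occurrence of grade 3 fever". The grade 3 limit given there is 39.0 °C, taken over from protocol section 10.8, where it is followed by "axillary temperature) with causal relationship to vaccination". SAP section 10.1.2.3.2 adds that a subject with a symptom marked present but no reading at all "will be assigned to the lowest intensity category at that dose (i.e., 37.5°C for fever or grade 1 for other symptoms").

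**The concern.** The rectal scale is meant to put all routes on one footing, yet its distance from the other scale is not constant: 0.5 °C at the entry to grade 1 and 1.0 °C at the next two limits. The only relation between routes that the protocol gives is the 0.5 °C in its fever definition, and the SAP does not explain the larger steps. Rectal is one of the two preferred routes, so the readings affected could be numerous.

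The increment table raises a second question. Its text names a grade 3 limit for axillary temperature and gives no instruction for rectal readings. Two programmers could fill the rows differently, and a rectal reading could appear as above 39.0 °C in one table and as grade 2 in another.

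At stake would be the meaning of the absolute rates of grade 2-or-higher and grade 3 fever. That matters in a study whose protocol notes more fever when the two vaccines are given together (section 6.6) and sends grade 3 general events to the monitoring committee (section 5.4.1).

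**Working it through.** **Limits side by side** (protocol section 8.2.3.2.1; SAP section 10.1.3.5)

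| Lower limit of | Oral, axillary, tympanic | Rectal | Difference |
|---|---|---|---|
| Grade 1 | ≥37.5 °C | ≥38.0 °C | 38.0 − 37.5 = 0.5 °C |
| Grade 2 | >38.0 °C | >39.0 °C | 39.0 − 38.0 = 1.0 °C |
| Grade 3 | >39.0 °C | >40.0 °C | 40.0 − 39.0 = 1.0 °C |

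The first difference equals the one in the protocol's fever definition, so the any-fever boundary is consistent across routes. Only the two 1.0 °C steps lack a source.

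**Does every reading have a grade?** Each scale runs from below its grade 1 limit to above its grade 3 limit, without gaps or overlaps at one decimal. Route decides which scale applies. Every reading therefore has exactly one grade, and the pooled rates are simple counts of those grades. SAP section 10.1 says its rules will be applied, so this is an operative instruction.

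**Would one constant offset reproduce the rectal scale?** Subtract a constant d from each one-decimal rectal reading from 37.0 to 41.5 °C, grade it on the non-rectal scale, and count disagreements with the SAP's rectal grade:

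| d | At grade ≥1 | At grade ≥2 | At grade 3 |
|---|---|---|---|
| 0.5 °C | 0 | 5 (38.6 to 39.0) | 5 (39.6 to 40.0) |
| 1.0 °C | 5 (38.0 to 38.4) | 0 | 0 |

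No constant among those tried (0 to 1.5 °C) removes all disagreement. This shows that the scale is not a fixed conversion. It does not show an error, because the SAP never says that it converts by a constant.

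**Increment rows against grades.** One-decimal rectal readings that would count as above 39.0 °C without being grade 3:

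- entered raw: 39.1 to 40.0 °C, 10 values
- after subtracting 0.5 °C: 39.6 to 40.0 °C, 5 values
- after subtracting 1.0 °C: none

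Entered raw, the 10 values from 38.1 to 39.0 °C would likewise count as above 38.0 °C while being grade 1.

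**Size.** The gap between the row above 39.0 °C and the grade 3 rate, caused by rectal readings, is p × q. Here p is the share of infants measured rectally and q is the share of those whose maximum falls in the discordant band. Neither is in the documents, so the values below are assumptions.

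- Raw entry, p 10 to 75%, q 2 to 10%: from 0.10 × 0.02 = 0.2 to 0.75 × 0.10 = 7.5 percentage points.
- 0.5 °C conversion, p 10 to 90%, q 1 to 5%: from 0.10 × 0.01 = 0.1 to 0.90 × 0.05 = 4.5 points; 0.045 × 680 = 30.6, about 31 of at most 680 infants.
- 1.0 °C conversion: 0.

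**Fever marked present without a reading.** The 37.5 °C named in SAP section 10.1.2.3.2 would be grade 0 on the rectal scale. The operative rule is the lowest intensity category, however, and the same section says "any missing daily recordings will be given imputed values to allow them to contribute to the" any-fever rows. Neither rule affects grade 2 or grade 3 counts.

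**The case for a change.** The strongest case for a change is that route-specific grades are supposed to mean the same thing once pooled, and the SAP asserts this without giving a basis for two of the three limits. The rectal scale sits in the standard-rules annex and is mentioned neither in the SAP's list of changes (section 8) nor in its additional safety considerations (section 5.4.2). Grade 3 general events go to the monitoring committee, and the protocol's risk table (section 1.3.1) lists 40.0 °C or more within 48 hours without naming a route, while a rectal 40.0 °C is grade 2. A sentence or a split by route would cost little, since scoring already needs the route.

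Part of this stands: the basis for the 1.0 °C steps is not stated, and the handling of rectal readings in the increment rows is not written down. The rest is weaker. Ordinal bands need not differ by one constant. The axillary limit in SAP section 5.4.1 agrees with the protocol scale for that route and says nothing against grading rectal readings on their own scale. The documents do not say which scale the committee uses; its working rules are in its charter. The mock fever table (Template 19) is headed axillary, but SAP Annex 3 says that mock titles and footnotes will be adapted according to a table list that is not included here. Conflict between rows and grades arises under raw entry or a small conversion, and nothing shows that the analysts would use either without a route label.

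**Conclusion.** The plan need not change. The grade 2-or-higher and grade 3 rates are fully determined by the protocol scale and the SAP's rectal scale together. The real gap is narrow: no stated basis for two 1.0 °C steps and no written rule for rectal readings in the 0.5 °C rows. Analysts can settle the rows in the table derivation by labelling by route or footnoting a conversion, and the choice between them is one of presentation. A split by route would also bring smaller denominators and wider intervals.

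Fever is a secondary safety outcome, all analyses are descriptive (SAP section 6), both groups are graded by the same rule, and no between-group bias is shown. No test, sample size or primary endpoint is touched. The size cannot be taken from the documents. The illustrations rest on assumed shares and on a handling of rectal readings that the SAP does not prescribe, and they include zero. The conclusion assumes that route is recorded with each temperature, which SAP section 10.1.3.5 already requires for scoring. No view is taken on which cut-offs are right.
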